## 1. Introduction

Septic shock is a leading global cause of pediatric death. In the US, the in-hospital mortality rate for children with sepsis is 5-20%. Septic shock is a state of critical infection that requires advanced and resource-intensive resuscitation, and morbidity-free survival depends on timely diagnosis. Critical care delivered in a delayed fashion, after a child is in hypotensive shock, is less effective; for each hour of unrecognized shock the odds of death more than double. Advances have been made in timely sepsis treatment, but improving diagnosis of septic shock in children remains elusive. Improved early diagnosis would accelerate treatment and improve outcomes.

Tools that have been deployed to improve diagnosis in pediatric sepsis either diagnose it after organ dysfunction criteria have been met, or depend heavily on subspecialty physician judgment and have not been tested outside of tertiary pediatric hospitals. Thus, the evidence-based 2020 Surviving Sepsis Children's Guidelines for pediatric sepsis stated that "high-quality trials on pediatric sepsis recognition are lacking, and data are not sufficient to suggest any particular screening tool," and identified pediatric sepsis recognition trials as an important research need. Despite this, the guidelines weakly recommended screening patients "who present as acutely unwell" for septic shock, citing very low quality evidence. The guidelines also stated that there is no evidence for the effectiveness of any existing pediatric sepsis screening tools.

This study addresses a gap in knowledge about the effectiveness of pediatric sepsis prediction tools. The study team has developed and retrospectively validated early diagnostic models that leverage clinical data in the Electronic Health Record (EHR) to predict septic shock in children in the emergency setting. In order to address concerns about alert fatigue and antibiotic overuse, these predictive models were designed to identify patients at high risk for shock among patients in whom clinicians initially had some suspicion for sepsis.

## 2. Study design

This study is a prospective, stepped-wedge cluster randomized trial to test the effectiveness of implementing a Clinical Decision Support (CDS) tool for prediction of septic shock in four Emergency Departments (ED) within a pediatric healthcare network. The site will be the unit of randomization. All ED providers at the site will receive the CDS intervention when their site receives the intervention. The outcomes will be measured at the patient level. There will be five, 10-week study periods and four sites. In the first period, no sites will receive the intervention. During each subsequent period, one site will crossover to receive the intervention.

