#### Minimal necessary sample size to fit the multivariable models

For the binary outcome of guideline-concordant care, the model for sensitivity analyses will have up to 9 degrees of freedom (intercept + 3 (4 sites) + 4 (five time periods) + 1 for treatment). Using the rule of tens, we must have at least 90 outcomes. In the worst case scenario, there will be no treatment effect and 25% of the sample should have the outcome. This yields a minimal needed sample of  $90/0.25 = 360$ . In a univariable test, assuming a minimal detectable difference of 0.25, The power attainable would be 99.9%.

In the event that the treatment and control groups are imbalanced for some covariates, and 5 parameters are added, approximately 140 outcomes will be necessary to fit the model adequately. Then the minimal sample size becomes:  $140/0.25 = 560$ . In a univariable test, assuming a minimal detectable difference of 0.25, The power attainable would be >99.9% under the expected sample size of 2054.

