## 6. Analyses

The primary hypothesis will test whether the proportion of patients receiving guideline-concordant septic shock care is greater in the intervention arm compared to the control arm. An odds ratio will be calculated to assess this, and will be considered significant if the 95% confidence interval does not contain 1.0.

Analyses will be conducted at the level of the patient encounter using the generalized linear model framework. The primary analysis will include an effect for intervention, and subsequent sensitivity analyses will include fixed effects for time and site to test for heterogeneity of effect. Up to five additional covariates will be included if they are imbalanced between the two arms of the trial. We will construct tables comparing the medians and proportions of clinically meaningful variables that might be expected to affect the association between the intervention and the outcome of guideline-concordant care. These potential covariates considered will include patient characteristics, provider type, arrival modality, triage level, and social determinants of health, including race, ethnicity, and insurance status. Standardized differences will be used to assess the magnitude of difference in covariates between arms. Anywhere that we find significant imbalance between arms, that variable will be included as a covariate.

Significance of effects will be assessed at the 5% level, with all tests structured as two sided hypotheses. SAS software version 9.4 (SAS Institute, Cary, NC) and R version 4 (R Foundation for Statistical Computing, Vienna, Austria) will be used for all data management and statistical analysis.

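### The site- and period-adjusted sensitivity model has one constant intervention term, so it cannot test for heterogeneity of effect and can be distorted if the CDS effect changes with time since go-live

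*SAP*

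**What the plan says.** SAP section 2 fixes the layout: "There will be five, 10-week study periods and four sites". Every site is under control at the start, and after that the sites switch one at a time: "During each subsequent period, one site will crossover to receive the intervention". Exposure at a site is all at once: "All ED providers at the site will receive the CDS intervention when their site receives the intervention". The SAP states no transition period.

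Section 6 defines two models for the primary outcome. In the first, "The primary analysis will include an effect for intervention", with no site or period terms. In the second, "subsequent sensitivity analyses will include fixed effects for time and site to test for heterogeneity of effect". The subsection on the minimal sample size for the multivariable models counts the parameters of this second model as "intercept + 3 (4 sites) + 4 (five time periods) + 1 for treatment", which is 9, one of them for treatment. Section 6.2 also gives the Cox model for time to antibiotics a single binary treatment term. No model contains a term for time since go-live.

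**The concern.** Time since go-live differs widely here: the first site to cross over contributes up to 40 weeks of CDS use, the last only 10. A single intervention term assumes the same effect in the first weeks as in the last. For an alert tool, uptake may build as staff learn it or fade as they tire of it.

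Two things follow.

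- The stated purpose of the adjusted model is to test for heterogeneity of effect. Site and time main effects shift the baseline rate but leave the intervention effect constant, so the model cannot serve that purpose.
- With both site and period effects in a stepped-wedge layout, already exposed cells act partly as comparators for newly exposed ones. If the effect changes with exposure, the single coefficient need not be a sensible average.

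The adjusted model is the only specified analysis that accounts for secular trend, so its agreement or disagreement with the primary model will affect whether the primary result is believed.

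**Working it through.** **Inputs.** From section 2: 4 sites, 5 periods, 20 site-period cells, period 1 all control, one crossover per period. Exposure periods 1, 2, 3 and 4 therefore occur in 4, 3, 2 and 1 cells, 10 exposed cells in all. From section 2.1: 2054 patients and a 25% control rate. Assumed, because the SAP does not give them: equal cells of 2054/20 = 102.7 patients, independent patients, and the effect patterns used below.

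**The plan's own figures.** 1 + 3 + 4 + 1 = 9 parameters; 9 × 10 = 90 outcomes; 90/0.25 = 360 patients. These reproduce. The design matrix has rank 9, so the model can be fitted.

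**Weights in the adjusted model.** With equal cells, the least-squares weight on cell (i, j) is

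w_ij = (x_ij − x̄_i − x̄_j + x̄) / Σ(x_ij − x̄_i − x̄_j + x̄)²

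where x is 1 if exposed. Site means are 0.8, 0.6, 0.4 and 0.2; period means are 0, 0.25, 0.5, 0.75 and 1; the overall mean is 0.5; the denominator is 1.5. Example, first site in period 2: (1 − 0.8 − 0.25 + 0.5)/1.5 = 0.45/1.5 = 0.3.

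Weights of the exposed cells, in thirtieths, summed by exposure period:

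| Exposure period | Cells | Sum | Adjusted weight | Intervention-only weight |
|---|---|---|---|---|
| 1 | 9 + 8 + 7 + 6 | 30 | +1.0 | 0.4 |
| 2 | 4 + 3 + 2 | 9 | +0.3 | 0.3 |
| 3 | −1 − 2 | −3 | −0.1 | 0.2 |
| 4 | −6 | −6 | −0.2 | 0.1 |

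The intervention-only weights are the shares of exposed cells: 4/10, 3/10, 2/10 and 1/10.

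**Effect of assumed patterns (percentage points, linear scale).**

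- 0, 10, 20, 30: adjusted 0 + 3 − 2 − 6 = −5; exposed-cell average 0 + 3 + 4 + 3 = 10.
- 20, 15, 10, 5: adjusted 20 + 4.5 − 1 − 1 = 22.5; average 8 + 4.5 + 2 + 0.5 = 15.
- 0, 25, 25, 25: adjusted 0 + 7.5 − 2.5 − 5 = 0; average 15.
- Constant 25: both give 25.

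**Logistic scale.** Logistic models fitted to expected counts from a 25% baseline show the same pattern. Effects of 6.25, 12.5, 18.75 and 25 points give an adjusted odds ratio of 1.17 against 1.80 unadjusted. Effects of 25, 20, 10 and 5 give 3.72 against 2.31. A constant 25 points gives 3.0 in both.

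**Unequal sites.** With assumed site volumes of 40, 30, 20 and 10% in any order, the first weight stays between 0.94 and 1.07 and the fourth between −0.30 and −0.10. The third stays near zero, from −0.18 to 0.01. With 60, 20, 10 and 10% the first weight is 0.93 to 1.08.

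**An alternative model.** Site, period and one indicator per exposure period is 1 + 3 + 4 + 4 = 12 parameters, and the matrix has rank 12. Standard errors are √(v × 0.25 × 0.75/102.7), with v from the inverse of X′X:

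- single-term model, v = 0.667: 3.5 points;
- exposure periods 1 to 4, v = 0.800, 1.435, 2.542, 4.690: 3.8, 5.1, 6.8 and 9.3 points;
- average weighted 0.4, 0.3, 0.2, 0.1, v = 1.248: 4.8 points.

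**The case against.** The strongest reply is that the affected model is only a sensitivity analysis. The primary model already weights exposure periods by exposed cells. With equal cells, no secular trend and no site differences, it recovers the averages of 10 and 15 points in the examples above. That stands, and it limits the point: nothing here shows the primary estimate to be wrong. But the primary model has this property only when there is no trend or site difference to adjust for, and that is what the adjusted model is meant to check.

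Second, a changing effect is assumed. Section 1 mentions alert fatigue as something the prediction models were designed to limit, not as a forecast. That also stands. The patterns above are illustrations, and under a constant effect there is no distortion.

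Third, a transition or training period may be set out in the protocol, which is not at hand. Its absence from the SAP is therefore no finding. The 9-parameter model in the SAP nevertheless uses all five periods with one treatment term.

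A reader might infer from the weight of 1.0 that the adjusted estimate measures only the first 10 weeks of use. The layout does not support that. The later weights sum to zero but cancel only if the later effects are equal or happen to balance. With effects of 0, 10, 20 and 30 the estimate is −5, while the first-period effect is 0.

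**Conclusion.** The point holds as a limitation of the adjusted sensitivity model. One constant term with site and time main effects cannot test for heterogeneity of effect, contrary to the purpose section 6 gives it. In this layout, net weight 1.0 falls on the first exposure period and −0.1 and −0.2 on the third and fourth. If the effect grows or wanes, the estimate can fall outside the range of the true effects, by amounts that depend on the pattern. The primary and adjusted models would then estimate different quantities, and a gap between them could be taken for secular trend when it reflects time since go-live.

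The weights are exact for a linear model with equal cells. They shift moderately with unequal site volumes, and the logistic model behaves similarly. Whether the effect varies at all is unknown. This is a cheap improvement to the plan, not a defect in the primary result.

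**What to change.** Keep the planned models and add one prespecified sensitivity model with site effects, period effects and one indicator for each of the four exposure periods. In the SAP:

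- report the average of the four effects, weighted 0.4, 0.3, 0.2 and 0.1 by exposed site-periods;
- use this model to test for heterogeneity by time since go-live, and correct the purpose now given to the site and time main effects;
- state that the single-term adjusted odds ratio is not read as the overall effect if the exposure-period effects differ.

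A shorter split into the first 10 weeks and all later weeks should not be the main remedy. Its first term keeps the weights 1.0, 0.3, −0.1 and −0.2, and its 0.4/0.6 average has weights 0.40, 0.78, 0.04 and −0.22. For effects of 0, 10, 20 and 30 that average is 7.8 + 0.8 − 6.6 = 2.0 against a true 10.

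The work is SAP wording and three more parameters, built from go-live and arrival dates. By the SAP's rule of tens, 12 parameters need 120 outcomes, or 120/0.25 = 480 patients, against 2054 expected. With the five optional covariates it is 170/0.25 = 680. The real cost is precision: about 4.8 points for the weighted average against 3.5 for the single term, and as much as 9.3 points for the fourth exposure period, which rests on one site. The new model is therefore a check on interpretation and will have limited power to detect modest variation.

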### 2.1 Sample size calculation

The unit of analysis for this study is ED patients with suspected sepsis. The necessary enrollment size was used to calculate the study period necessary to achieve power, based on historic volume trends. The main calculations were done using the `pwr` package for R.

During the study period, we expect 2054 patients to be identified and exposed to decision support (CDS). With current care patterns, we would expect 25% (514) to receive guideline-

concordant septic shock care prior to shock occurring. In the literature, use of pediatric sepsis quality interventions has increased rates of concordant early care of shock to 50% (1027). With an estimated effect of the alert of increasing rates of concordant care from 25% to 50%, using a significance of 0.05, we anticipate >90% power to detect this difference. We will have 80% power to detect an increase of 6%.

For the outcome of time to receipt of antibiotic, we expect that 79% of patients will receive antibiotics. Among those who do receive antibiotics, with current care patterns, in pilot data we have observed a mean time to antibiotics of 55 minutes, or a mean log time of 4.0 (SD 1.29). In published pediatric sepsis literature, the use of pediatric sepsis quality interventions has decreased the log time to antibiotic to 3.3 (SD 1.54). Using a significance of 0.05, we anticipate >90% power to detect a difference in this outcome. We have 80% power to detect a smaller difference of 4.0 vs 3.8 (55 to 45 minutes). Even under conditions of very slow accrual where half of the hypothesised sample is realized, we would have 80% power to detect a difference of 4.0 vs 3.72 (55 to 41 minutes).

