### 6.2 Secondary outcomes (continuous – time to antibiotic)

The secondary hypothesis will test whether the time to antibiotics is shorter in the intervention arm compared to the control arm. A hazard ratio will be calculated to assess this, and considered significant if the 95% confidence interval does not contain 1.0. The following approach will be used.

Time will be measured beginning with admission to the ED and concluding with administration of antibiotics (an event) or discharge from the ED (censoring). Death is expected to be rare and will be treated as a censoring event. Analysis will use a Cox proportional hazard model with a fixed binary effect for treatment.

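### The three 80% power statements for small effects in SAP Section 2.1 hold only for an unadjusted comparison with no secular trend; with the site and period effects of the stepped wedge, power for a 6-point gain is about 38%

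*SAP*

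**What the plan says.** Section 2 describes four sites and five 10-week periods, with no site exposed in the first: "During each subsequent period, one site will crossover to receive the intervention".

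Section 2.1 takes its main calculations from the R package `pwr` and mentions no site effect, period effect or intracluster correlation (ICC). It makes three small-effect statements:

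- guideline-concordant care: "We will have 80% power to detect an increase of 6"%;
- log time to antibiotics: "We have 80% power to detect a smaller difference of 4.0 vs 3.8 (55 to 45 minutes");
- log time at half accrual: "we would have 80% power to detect a difference of 4.0 vs 3.72 (55 to 41 minutes").

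The sample is introduced with "During the study period, we expect 2054 patients to be identified and exposed to decision support (CDS").

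The subsection on minimal sample size counts site and period parameters, but for another purpose: "the model for sensitivity analyses will have up to 9 degrees of freedom". Section 6 confirms the order: "The primary analysis will include an effect for intervention, and subsequent sensitivity analyses will include fixed effects for time and site". For time to antibiotics, Section 6.2 has neither site nor period: "Analysis will use a Cox proportional hazard model with a fixed binary effect for treatment".

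**The concern.** Control observations come mostly from early periods and intervention observations mostly from late ones. An unadjusted comparison therefore adds any change in care over the 50 weeks to the tool's effect. Period effects remove a common trend and site effects remove differences between sites, but both use up information because exposure is correlated with each. The SAP writes down the model that does this and never states its power.

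The three statements tell readers that the trial can detect modest effects even if recruitment halves. If that is true only of an analysis open to drift, the reassurance is misplaced. A null adjusted result could also be misread as evidence against a small effect.

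**Working it through.** **Inputs from the SAP.** N = 2054; control rate 25%; two-sided 5% level; 79% receive antibiotics; log-time SDs 1.29 and 1.54; four sites, five periods, one crossover per period. **Assumed:** equal sites and periods unless stated otherwise.

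**1. Reproducing the stated figures.** With equal sites, 10 of 20 site-periods are exposed, so there are 1027 patients per condition. The arcsine test used by `pwr` has h = 2·arcsin√0.31 − 2·arcsin√0.25 = 0.134 and power Φ(h√(n/2) − 1.96).

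- n = 1027: Φ(3.03 − 1.96) = 86% for exactly 6 points. 80% power is reached at 5.5 points, which rounds to the stated 6.
- Log time: 0.79 × 2054 = 1623 patients, about 811 per condition. SD = √((1.29² + 1.54²)/2) = 1.42. For 0.20: 0.20/(1.42·√(2/811)) = 2.84, power 81%.
- Half accrual: 406 per condition, difference 0.28, power 80%.

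So the figures are correct as two-group tests, provided 2054 is the total. With 2054 in each condition, 6 points would have 99% power.

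**2. Information left after adjustment.** Sums of squares of the treatment indicator over the 20 site-periods:

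- total: 20 × 0.5² = 5.0;
- between periods (exposed shares 0, ¼, ½, ¾, 1): 4 × 0.625 = 2.5;
- between sites (exposed shares 0.8, 0.6, 0.4, 0.2): 5 × 0.20 = 1.0;
- left after both: 5.0 − 2.5 − 1.0 = 1.5, that is 1.5/5.0 = 0.30.

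The effective size is 0.30 × 1027 = 308 per condition.

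**3. Power for 25% vs 31%.**

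| Model (equal sites unless stated) | Power | Gain detectable at 80% |
|---|---|---|
| Unadjusted | 86% | 5.5 points |
| Period only, no site differences (factor 0.50) | 57% | 7.9 points |
| Period, random site, ICC 0.001 (assumed) | 51% | – |
| Fixed site and period (factor 0.30) | 38% | 10.3 points |
| ICC 0.03, autocorrelation 0.8 (assumed) | 27% | 12.5 points |
| Fixed site and period, assumed shares 50/25/15/10, all orders | 32–36% | – |

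A logistic simulation with site and period effects (10,000 runs) gave 38.5% for 25% vs 31%.

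**4. Log time at factor 0.30** (t-test approximation in treated patients).

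- 243 per condition, 0.20: 0.20/(1.42·√(2/243)) = 1.55, power 34%. It is 40% at SD 1.29 and 30% at SD 1.54. The difference detectable at 80% is 0.33–0.36 (SD 1.29–1.42), or 55 to about 38–40 minutes.
- Half accrual, 122 per condition, 0.28: 34% (39% at SD 1.29, 29% at SD 1.54). The detectable difference is 0.46–0.51.

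**5. On the Cox scale** the hazard ratio detectable at 80% is exp(2.80/√(D × 0.25 × f)). With D = 1623 events it is 1.15 at f = 1 and 1.29 at f = 0.30. With D = 811 it is 1.22 and 1.43.

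**6. Does the unadjusted model save the 80%?** Exposed site-periods fall on average two periods later than control ones. Assume a linear background rise of 4 points from first to last period (1 per step) and no tool effect. The bias is 2 points against a standard error of about √(2 × 0.27 × 0.73/1027) = 0.0196, so about 18% of trials are significant. A 6-point rise gives a 3-point bias and about 33%. Simulation gave 18% and 34% unadjusted, and 5% with site and period effects.

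**7. Planning effects.** 25% vs 50% and 4.0 vs 3.3 both keep more than 99.9% power at factor 0.30 (SD 1.42 for log time). At an assumed ICC of 0.1 and autocorrelation 0.8, 25% vs 50% keeps about 94–95%.

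**The case against.** The strongest reply is that nothing is miscalculated. Section 2.1 powers the analysis that Section 6 names as primary, the SAP calls its companion checks univariable, and it nowhere claims 80% for the sensitivity model. The trial is sized on 25% vs 50%, which survives, so the small-effect sentences are supplementary. All of this is true. It makes the point a mismatch between power statement and design; the trial is not underpowered for its planning effect. It does not make the 80% usable, because the model it belongs to cannot tell a 6-point effect from modest drift.

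Three narrower points also stand.

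- The ICC and autocorrelation values are assumptions, so 27% to 57% is not a bound. ICC 0.1 with autocorrelation 0.8 gives about 15%.
- The drifts of 4 and 6 points illustrate a risk. They do not estimate this trial's error rate.
- If 2054 really meant exposed patients only (4108 in total), power would be 65% with fixed site and period effects and 86% with period effects alone. The total reading is the one that reproduces the stated figures.

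Period effects alone would remove a common trend, but that is the best case and still gives only 57% with 2054 in total.

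**Conclusion.** The concern holds. The three 80% statements describe an unadjusted comparison and are valid only with no secular trend. For the site-and-period model, power is about 38% for 6 points and about 34% for each log-time statement at SD 1.42. These values rest on the SAP's own inputs plus equal site sizes; the unequal shares examined lower the 38% to 32–36%. With 2054 in total, no adjusted setting examined reaches 80%. The statements of more than 90% power for the planning effects are sound.

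Two wording faults belong to the same calculation. The 2054 are called exposed although the figures need them to be the total. The time figures are t-tests on log time in treated patients, whereas a Cox model is planned.

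**What to change.** - Recompute the three small-effect statements for the model with site and period effects. Report a range over stated site shares (from the historic volumes already used), ICC and autocorrelation.
- Name that model for inference in Section 6 and add site and period to the Cox model in Section 6.2, so that power and analysis agree. If the intervention-only model stays primary, label the 80% figures as unadjusted and valid only without a secular trend, and print the adjusted range beside them.
- Mark the log-time figures as a t-test approximation in treated patients, or replace them with a detectable hazard ratio.
- Describe 2054 as the total across control and intervention periods and give the expected share exposed: 50% with equal sites, 37–63% with shares 50/25/15/10 depending on the randomised order.
- Keep the statements of more than 90% power.

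The cost is a recalculation and a few sentences in Sections 2.1 and 6, with no extra patients and no design change. The downside is that the detectable differences look less favourable, and if there is truly no trend the adjusted model gives up power.
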